12.7 Incidence of eye exam findings

Incidence of patients with any new finding on ophthalmological examination in the follow up period will be calculated. Detailed listings of all baseline and on-treatment ophthalmological findings will be provided

Incidences will be calculated using the number of patients in the safety population as denominator.

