- Incidence of positive psychotic symptoms (BPRS+) findings from screening/baseline to the end of the 2-week and the 6-week treatment period and safety follow-up
- Incidence of physical examination, vital signs and laboratory tests findings (haematology and biochemistry)
- Incidence of cardiovascular safety findings (blood pressure, heart rate, ECG including QT/QTc)
- Incidence of eye exam findings

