# **8.4.1.13** Eye Examination

An eye examination will be performed at screening and after study treatment completion or early termination. This will include a full ocular check (lids, conjunctiva, sclera, cornea, anterior chamber, pupil, iris, and lens) and any abnormalities will be noted. Additional eye examinations may be performed at the discretion of the investigator during follow-up. An ophthalmologist will evaluate the findings and any abnormality will be recorded in the subject clinical notes as either medical history (findings at screening) or any further finding or change from screening after completion of study treatment. A specific eye exam procedure guidance document will be prepared for the study in order to harmonize the examination..

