#### 8.4.7 **Safety Variables**

Safety variables will include:

- Incidence of Adverse Events (AEs) and Adverse Events of Special Interest (AESIs) like headache, nausea and insomnia
- Incidence of physical examination, vital signs and laboratory tests findings (haematology and biochemistry)
- Incidence of cardiovascular safety findings (blood pressure, heart rate, ECG including QT/QTc)
- Incidence of suicidal ideation (C-SSRS) findings from screening/baseline to the end of the 2-week and the 6-week treatment period and safety follow-up
- Incidence of positive psychotic symptoms (BPRS+) findings from screening/baseline to the end of the 2-week and the 6-week treatment period and safety follow-up
- Incidence of eye examination findings

Amendment 04, Final Version 1.0 07/Nov/2018 Page 64 / 142

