### 11.1.7 Safety Analyses

Adverse events, adverse events of special interest, serious adverse events, serious and related adverse events will be coded using the latest available MedDRA version and their corresponding incidences will be summarised as overall events, related events, and events by intensity. AEs will be summarised by MedDRA preferred term and system organ class (primary SOC). Summaries of AEs by preferred term and decreasing frequency and by maximum severity will also be prepared.

Physical examination changes, vital signs changes, laboratory tests changes, cardiovascular changes, ocular changes, suicidal ideation (C-SSRS) findings, and positive psychotic symptoms (BPRS+) findings will be described for the different treatment groups and assessed as either clinically or non-clinically significant findings.

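### SAP 12.7 counts only new eye findings, which is narrower than the changes from screening that the protocol records and plans to describe by treatment group, and SAP 14 does not declare the narrowing

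*SAP*

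**What the plan says.** **Protocol**
- The endpoint in 6.2.2 reads only "Incidence of eye exam findings", and the safety variable in 8.4.7 reads "Incidence of eye examination findings". Neither says whether a finding must be new, worse or merely present.
- Section 8.4.1.13 sets the content of the examination: "full ocular check (lids, conjunctiva, sclera, cornea, anterior chamber, pupil, iris, and lens) and any abnormalities will be noted". An ophthalmologist evaluates the result. Abnormalities at screening are recorded as medical history. Afterwards the record is to cover "any further finding or change from screening after completion of study treatment". The place of recording is the subject's clinical notes.
- Section 11.1.7 sets the analysis: "cardiovascular changes, ocular changes, suicidal ideation (C-SSRS) findings, and positive psychotic symptoms (BPRS+) findings will be described for the different treatment groups". It also requires each to be assessed as clinically significant or not.

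**SAP**
- Section 12.7 gives one summary: "Incidence of patients with any new finding on ophthalmological examination in the follow up period will be calculated". The denominator is the safety population. Listings of baseline and on-treatment eye findings are added.
- Section 11, the list of safety endpoints, does not mention the eye examination, so 12.7 is its only definition.
- Section 14 states that nothing statistical differs from the protocol.

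**The concern.** The protocol's recording rule names two things joined by *or*: a further finding, and a change from screening. Its analysis section speaks of changes. The SAP keeps a count of new findings and says nothing about an abnormality that was already there and became worse.

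Subjects are 50 to 80 years old. Exclusion criterion 2 removes significant eye disease that affects mobility and the ability to be examined, so a subject with a lesser abnormality can enter. Amendment 02 removed lens grading and left this examination as the scheduled ocular safety assessment, and the trial has no data monitoring committee. If worsening is not counted, the only by-arm eye table would omit one of the two kinds of change that the ophthalmologist is asked to record. A reader of the study report could take that table as a complete summary of ocular change.

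**Working it through.** The documents state no ocular rate, so there is no planned figure to reproduce. The check is a comparison of texts.

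**1. Apply both rules to the possible cases.**

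| Screening | After treatment | Recorded under protocol 8.4.1.13? | Counted in SAP 12.7, read plainly? |
|---|---|---|---|
| Normal | Abnormal | Yes, further finding | Yes |
| Abnormal lid | Same lid, plus a corneal abnormality | Yes, further finding | Yes |
| Abnormal lens | Same lens abnormality, worse | Yes, change from screening | No |
| Abnormal lens | Unchanged | No | No |

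The rules part only in the third row.

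**2. See whether the SAP handles worsening elsewhere.** It generally says so where it means to count it. Section 12.1 treats worsening as an onset of an adverse event. Section 12.3 reports rises and falls in BPRS+. Section 12.5 has laboratory shift tables. Section 12.6 has change-from-baseline limits for blood pressure and heart rate. The physical examination in 12.4 is confined to normal-to-abnormal shifts, but that limit is written out. Section 12.7 has no worsening rule, no shift table, no definition of *new* and no split by clinical significance.

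**3. Follow the third-row subject through the other outputs.**
- Listings: the subject appears, but a listing gives no incidence by arm.
- Adverse event tables: protocol 9.1.1 and 9.1.2 make worsening of a pre-existing condition an adverse event. For degenerative conditions, with cataract as a named example, 9.1.2 restricts this to worsening beyond what would be expected. Protocol 8.4.1.12 has later ECG changes entered in the eCRF as adverse events, whereas 8.4.1.13 gives no such instruction for the eye. Some worsening may reach these tables, but not all of it need do so.

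**4. Size.** The number of subjects per arm left out is at most N × q × w, where q is the share with an eye abnormality at screening and w the chance that it worsens. It is an upper value because a subject who also has a new finding is counted anyway. N is about 230 / 4 = 57.5. The documents give neither q nor w. Purely as assumptions, with q from 10% to 60% and w from 1% to 10%:
- low end: 57.5 × 0.10 × 0.01 = 0.06 subjects per arm
- high end: 57.5 × 0.60 × 0.10 = 3.45 subjects per arm

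The assumed range runs from practically none to about three subjects per arm. It shows scale only, and nothing below depends on it.

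**The case against.** The strongest reply is that the SAP never says worsening is excluded. *New* is undefined, and protocol 9.1.1 itself treats a pre-existing problem that worsens on treatment as a new adverse event, so a programmer could count a worsened lens as new. That stands in part: the exclusion is an inference. But SAP 1 says the plan should be exact enough to guide programming, and a numerator that two programmers could build differently does not meet that aim.

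Second, safety is descriptive, all findings are listed, and adverse events are tabulated by group. A reader might infer that worsening disappears from the report. The documents do not support that. What is missing is the by-arm eye incidence for this kind of change.

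Third, the practical effect may be slight. Amendment 02 judges cataract development over six weeks very unlikely, and protocol 7.2 says subjects with ophthalmological impairment will not be entered. Both points stand and limit the expected number of events. The 7.2 statement is broader than exclusion criterion 2, which is the rule that sites apply.

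Fourth, the data may not be ready to use. Findings go to the clinical notes, and 8.4.1.13 sets no severity grade. That stands, and it is part of the cost of the change.

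**Conclusion.** The SAP numerator, read plainly, is narrower than what the protocol records and plans to describe by group, and the narrowing is undeclared. Worsening of an abnormality present at screening would reach the listings, and the adverse event tables if reported as an adverse event, but not the by-arm eye incidence. This rests on the ordinary meaning of *new* and on the absence of any other rule in the SAP.

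Two stronger readings should be avoided:
- A reader might infer that the protocol's endpoint itself covers change from screening. It does not. The endpoint names only eye findings; the wording about change belongs to the recording rule, and the reference to ocular changes belongs to the analysis section.
- A reader might infer that a definite share of ocular changes is lost, for instance by scaling a true change rate by the share of subjects with normal eyes at screening. The documents give neither quantity. The scaling is also wrong, because a subject with one abnormality at screening can still have a new finding elsewhere in the eye and would be counted.

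The size is therefore unknown and may be small. The point is worth correcting because the correction is cheap, not because it threatens the trial's main conclusions.

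**What to change.** In SAP 12.7, define the event as either (a) a finding absent at screening or (b) a worsening, recorded by the ophthalmologist, of a finding present at screening. Show (a) and (b) on separate rows for each arm, with the clinical-significance assessment that protocol 11.1.7 calls for. Keep the listings. If the sponsor prefers to count new findings only, define *new* in 12.7 and declare the narrowing in SAP 14.

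The cost is a few table rows. Before unblinding, someone must also confirm that the change-from-screening record, which the protocol places in the clinical notes, is in the database. If it is not, it has to be entered. No severity grading is needed, because the event rests on the ophthalmologist's recorded judgement that the finding is worse.

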13 OTHER ANALYSES

13.1 Demographic and Baseline Characteristics

Demographic characteristics, age, gender and race will be summarized by treatment group and overall using descriptive statistics. Age will be summarized using the number of available data, mean, standard deviation (SD), median, minimum and maximum and 95%CI whenever needed for each treatment group. Gender and race will be summarized using the number and percentage of patients in each treatment group.

The baseline value is defined as the last available value prior to the randomization.

All baseline safety and efficacy parameters are presented along with the summary statistics in the efficacy and safety sections (Section 9. and Section 11.).

13.2 Prior or Concomitant Medications

All medications taken within the past 4 weeks before the date of informed consent and until the end of the study are to be reported in the case report form pages.

All medications will be coded using the World Health Organization-Drug Dictionary (WHO-DD_Sep2017) and will be presented in the analysis by the Anatomic and Therapeutic Class.

Prior medications are those the patient used within 4 weeks prior to the date of informed consent and from screening to first investigational medicinal product (IMP) intake. Prior medications can be discontinued before first administration or can be ongoing during treatment phase. Those ongoing will be considered as Concomitant medication also.

Concomitant medications are any treatments received by the patient after first intake of IMP. A given medication can be classified both as a prior medication and as a concomitant medication.

13.3 Prohibited Medication

The following primary PD medications will be permitted at any time during the study if taken as stable medication for at least 4 weeks before screening (date of IC signature):

- Dopaminergics
- L-dopa
- Monoamine oxidase inhibitors (MAOI)
- Short-acting antipsychotics if taken in the evening
- Catechol-O-methyl transferase (COMT) inhibitors
- Amantadine if not used as an alerting agent

At a minimum, the following medications will be prohibited at any time during the study:

- Alerting agents, including r-modafinil, modafinil or methylphenidate
- Benzodiazepines
- Histamine active agents
- Hypnotics

- Cholinergics
- Skeletal muscle relaxants
- Clozapine
- Atomoxetine
- Amitriptyline
- Any other daytime medications which affect sleep

13.4 Medical History

All Medical History will be coded to a lower-level term (LLT), preferred term (PT), high-level term (HLT), high-level group term (HLGT), and associated primary system organ class (SOC) using the version of Medical Dictionary for Regulatory Activities (MedDRA) version 20.1. Number of patients with at least one medical history and percentage in each HLT will be presented by SOC. Denominator used for percentage calculation will be the number of patients in the SAF population.

13.5 Extent of investigational medicinal product exposure and compliance

Average number of doses taken per day will be calculated. Percentage of patients will be obtained for each of the categories defined below:

- <0.9 average doses/day taken
- ≥ 0.9 and <1.1 average doses/day taken
- ≥ 1.1 average doses/day taken

Duration of IMP exposure is defined as last dose date – first dose date, regardless of unplanned intermittent discontinuations. Duration of IMP exposure will be summarized descriptively as a quantitative variable (number, mean, SD, median, minimum, and maximum).

In addition, duration of treatment exposure will also be summarized categorically by numbers and percentages for each of the following categories and cumulatively according to these categories: Up to 1 weeks, >1 to 2 weeks; >2 to 3 weeks; >3 to 4weeks; >4 to 6 weeks; >6 weeks

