# Treatment Visit 3 (Day 42 ±3)

This visit will be performed 6 weeks after the 1st treatment administration (Day 1). The following examinations/procedures will be performed:

- Physical examination
- Vital signs
- Laboratory (haematology, biochemistry), serum pregnancy test (for women of childbearing potential)
- Electrocardiogram, heart rate, blood pressure
- Assessment of sleepiness scales: ESS, SCOPA-Sleep, PDSS-2
- Maintenance of Wakefulness Test (MWT)

Protocol No.: BB-2001-201b EudraCT No.: 2017-000877-35 Amendment 04, Final Version 1.0 07/Nov/2018 Page 61 / 142

- Polysomnography
- Cognitive assessment (MoCA)
- Columbia-Suicide Severity Rating Scale (C-SSRS)
- Fatigue assessment (FSS)
- Other scales: UPDRS Part III, HAM-D and BPRS+
- Wrist-worn actigraphy assessment 7 days continuously **before** last dose (day 35 to day 42).
- Wrist-worn actigraphy device return
- Drug return and accountability
- Recording of adverse events
- Recording of concomitant medication
- Eye examination (should be performed after the last treatment on Day 42 and before the follow up safety call)

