### 8.6.3 Dosages and Regimen

Each subject who qualifies for the study will receive wallet cards containing tablets of double-blind study medication. Subjects will receive 1 wallet card of their assigned treatment at Visit 1 (for 2 weeks treatment period) and 2 wallet cards at Visit 2 (for 4 weeks treatment period).

Subjects will be instructed to take 1 tablet orally per day at the same time in the morning, with or without food. The first dose is to be taken the day after randomisation when study medication has been dispensed to the subject.

The investigator or designee must instruct the subject to bring each of their study medication containers (wallet cards) to each clinic visit, regardless of whether the study medication cards are empty.

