#### 18.15. Schedule of Assessments

VISITS Week	Screening period (W-4)	Baseline period (W-1)	Randomisation Visit 1	Treatment Visit 2 (W2)		Treatment Visit 3 or Early Term (W6)	FUP (1)
Study days (referred to D1 [Day of first administration]	D-28 to D-8	D-7 to D-2	D-1	D14 (± 2)	D35	D42 (± 3)	+D28 (± 2)
(allowed deviation days in brackets)							
Informed consent	X						
Inclusion and exclusion criteria	X	$X^{(3)}$	X 				
Demographics	X						
Medical history and previous medication	$X^{(4)}$	X					
Concurrent Medical Condition	X						
Physical examination	X					X	
Vital signs (including heart rate and blood pressure)	X			X		X	X
Pregnancy test	X		X 			X	
Laboratory tests	X	X 				X	
Pharmacogenomic blood sample	X 						
Electrocardiogram	X					X	
Eye examination	X					X 	
Epworth Sleepiness Scale (ESS)	X		X	X		X	
Scales for Outcome in Parkinson's Disease Sleep (SCOPA-Sleep)			X	X		X	
Parkinson's Disease Sleep Scale (PDSS-2)			X	X		X	
Fatigue Severity Scale (FSS)	X					X	
Berlin Questionnaire (BQ)	X						
Unified Parkinson's Disease Rating Scale (UPDRS Part III) 			X	X		X	
Cognitive Impairment (Montreal Cognitive Assessment – MoCA	X					X	
Hamilton Rating Scale for Depression (HAM-D) $^{(10)}$	X			X		X	X
Columbia-Suicide Severity Rating Scale (C-SSRS) (10)	X			X		X	X
Brief Psychiatric Rating Scale positive subscale (BPRS+) 	X			X		X	X
Maintenance of Wakefulness Test (MWT) 		X				X	
Polysomnography 		X				X	
Free living activity (GENEActiv ®)(2)		X	X		X	X	
Randomisation			X				
Treatment intake 				X	X	X	
Adverse Events		X	X	X	X	X	X
Concomitant medication		X	X	X	X	X	

- (1)All subjects will perform a safety follow-up visit 28 days after last study visit performed.
  - Additional unscheduled visits may be arranged in case of eye examination, ECG, or adverse event findings.
- (2) GENEActiv® to be worn for 7 days continuously on the non-dominant hand day -7 to day -1 at baseline and before the last dose, day 35 to day 42.
- (3) Inclusion / Exclusion criteria to be reconfirmed before randomisation
- (4) Prohibited medical history will be assessed 4 weeks before Screening D-28
- (5) Dipstick pregnancy test to be completed before randomisation
- (6) If there are more than 14 days between screening and baseline

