- (7) Pharmacogenomic blood sample to be obtained in subjects who specifically consented for this exploratory analysis.
- (8) The eye examination should be performed after the last treatment on Day 42 and before the follow up safety call.
- (9) Subjects will be instructed to have already taken their normally scheduled dose of anti-parkinsonian medication and their IMP prior to arriving at the study site in order to have their UPDRS Part III evaluated in ON (within approximately 1 to 3 hours after taking their levodopa dose). UPDRS in OFF will not be evaluated.
  - It is recommended that all assessment (s) establishing eligibility for the study to be performed first.
- (10) Any positive finding on the HAM-D, C-SSRS, or BPRS+ scales during the study will be referred to a trained mental health professional to be followed.
- (11) MWT and Polysomnography will be performed on a minimum of 50% of subjects (all recruited in sites with sleep units available)
- (12) Treatment will be taken from Day 1 to Day 42, both inclusive.

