4 DESIGN OF THE STUDY

This phase 2b study is designed as multicentre, multinational, randomized, double blind, parallel group and placebo controlled with three doses of Bavisant (0.5, 1, and 3 mg/d) in subjects with excessive daytime sleepiness with Parkinson's disease. This study will involve approximately 230

subjects from around 48 sites globally. Eligible subjects will be randomly allocated at a ratio of 1:1:1:1 to either Bavisant (at doses of 0.5, 1 and 3 mg/d) or placebo. After signing the study informed consent, subjects meeting the UK PDS Brain Bank Clinical Diagnostic Criteria for Parkinson's disease (see details in the protocol Appendix 18.2) will enter a screening period (lasting up to 3 weeks) followed by a baseline period (lasting up to 1 week). Key inclusion / exclusion criteria will be verified to determine subject eligibility at the screening, baseline periods and prior to randomisation, including the suicide risk assessment following the FDA Guidance for Industry on Suicidal Ideation and Behavior. There is a 6 weeks treatment period, starting on Day 1, followed by a safety follow-up at least 4 weeks after completion of the treatment period. Additional unscheduled visits may be required based on the investigators' judgement at the end of study visit or at the safety follow-up. For early termination, all the assessments of the treatment week 6 visit should be performed, if possible, including the safety follow-up 4 weeks after the last investigational medicinal product (IMP) administration. The figure below describes the study flow graphically.

Figure 1

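### SAP 13.5 measures exposure as last dose date minus first dose date, one day short of the inclusive count for every subject

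*SAP*

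**What the plan says.** SAP 13.5 gives the rule: "Duration of IMP exposure is defined as last dose date" minus the first dose date, whatever unplanned interruptions fall in between. The closing clause deals with gaps in dosing and says nothing about whether both end days are counted. No other part of the SAP or protocol adds a day.

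The same section summarises the duration as a continuous variable (number, mean, SD, median, minimum, maximum) and in weekly categories: "Up to 1 weeks, >1 to 2 weeks; >2 to 3 weeks; >3 to 4weeks; >4 to 6 weeks; >6 weeks".

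The length of treatment is fixed elsewhere. The header of the schedule in protocol Appendix 18.15 makes D1 the day of first administration, and its footnote 12 reads "Treatment will be taken from Day 1 to Day 42, both inclusive". Protocol 8.6.3 sets the frequency: "Subjects will be instructed to take 1 tablet orally per day at the same time in the morning". SAP section 4 agrees on the length: "There is a 6 weeks treatment period, starting on Day 1". SAP section 6 puts anyone with at least one dose in the safety population.

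SAP 13.5 also asks for average doses per day, with cut-points at 0.9 and 1.1, and does not state the denominator.

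**The concern.** Subtracting two dates gives the elapsed time between them, which is one less than the number of calendar days from first to last dose counting both ends. With once-daily dosing numbered from Day 1, the natural measure of exposure is the inclusive count. The SAP rule therefore disagrees with the documents' own description of a six-week course.

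At stake is the accuracy of the exposure table in the study report. A subject treated exactly as planned would appear one day short of six weeks. The minimum could read 0 days in a population defined by having been dosed. Some subjects would be counted in the wrong weekly band. SAP section 1 says the plan should be precise enough to guide programming, so the formula is likely to be coded literally.

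**Working it through.** **Inputs.** First dose on Day 1, last planned dose on Day 42, both days included (protocol 18.15); one tablet a day (protocol 8.6.3); Visit 3 at Day 42 ± 3, that is Day 39 to Day 45 (protocol 8.4.2); category limits of 1, 2, 3, 4 and 6 weeks, that is 7, 14, 21, 28 and 42 days (SAP 13.5); smallest exposure in the safety population, one dose (SAP section 6).

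**Planned figure.** Day 1 to Day 42 inclusive: 42 - 1 + 1 = 42 days = 6 × 7. This matches the six-week treatment period.

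**SAP rule.** Last minus first: 42 - 1 = 41 days. This does not reproduce the planned 42. The gap is 1/42 = 2.4% of a full course.

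**Rule by last dosing day L.** The SAP gives L - 1 and the inclusive count gives L.

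| Last dose | SAP rule (days) | Category | Inclusive (days) | Category |
|---|---|---|---|---|
| Day 1 | 0 | up to 1 week | 1 | up to 1 week |
| Day 8 | 7 | up to 1 week | 8 | >1 to 2 |
| Day 15 | 14 | >1 to 2 | 15 | >2 to 3 |
| Day 22 | 21 | >2 to 3 | 22 | >3 to 4 |
| Day 29 | 28 | >3 to 4 | 29 | >4 to 6 |
| Day 42 | 41 | >4 to 6 | 42 | >4 to 6 |
| Day 43 | 42 | >4 to 6 | 43 | >6 |
| Day 45 | 44 | >6 | 45 | >6 |

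Checking every last dosing day from 1 to 59, the category changes only at Days 8, 15, 22, 29 and 43. Day 43 lies inside the Visit 3 window, and protocol 8.6.2 supplies surplus tablets for visit windows, so a last dose on that day can occur even though the planned course ends on Day 42.

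**Summary statistics.** Subtracting a constant of 1 from every value lowers the mean, median, minimum and maximum by 1 day. It leaves the SD unchanged. Because the constant is the same in all four arms, differences between arms in mean duration are also unchanged.

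**The case against.** The fair case against is that the formula is explicit and reproducible. It measures elapsed days, the offset is a known constant, and a reader who knows this can add one day. The SAP nowhere promises that a completer will be reported as 42 days. Nothing else uses this duration: no analysis set, efficacy model or treatment-emergent rule, and adverse-event percentages use the number of subjects in the safety population. Early drop-outs are not lost, since a single-dose subject is still counted in the lowest category. All of this stands as a limit on importance. It does not rescue the rule, because the table would be labelled as duration of exposure and cut at whole weeks of a course that the protocol counts inclusively.

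A reader might infer something stronger: that fully adherent early drop-outs will be labelled as over-dosed, because the too-short duration will serve as the denominator for average doses per day. On that assumption n daily doses would score n/(n - 1). This is undefined for one dose and at least 1.1 for 2 to 11 doses (11/10 = 1.100; 12/11 = 1.091). The documents do not support that reading. The doses-per-day item comes before the duration definition in SAP 13.5 and nothing links the two. The only denominator the documents state for tablets taken over time is the number of days between visits, in the compliance formula of protocol 8.6.10. With Visit 1 on Day -1 and the first dose the next day, an on-schedule Visit 2 on Day 14 comes 14 days after Visit 1 with 14 planned doses, so 14/14 = 1 and there is no inflation. What remains is only that the SAP does not name its denominator.

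**Conclusion.** The point holds as a minor error in a stated rule. It rests on Day 1 being the first dosing day and on exposure meaning the calendar span from first to last dose, both days counted and interruptions ignored. Neither the number of subjects stopping on the five affected days nor the number with a single dose can be known from the documents, so the count of misclassified subjects cannot be given. Efficacy results, power and type I error are untouched. The over-dosing consequence should not be claimed.

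**What to change.** In SAP 13.5, define duration of exposure as last dose date - first dose date + 1. This is a one-line edit that needs no new data and changes no study procedure.

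In the same section, state the denominator for average doses per day and reconcile it with the visit-interval formula in protocol 8.6.10, either by adopting that formula or by saying why a different one is used. Whichever is chosen, it should not be the uncorrected duration. This costs one further sentence.
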